## **Protocol for Personalizing MPK Prescription for Individuals With Transfemoral Amputation**

### **1. Study Aim, Background and Design**

**Background:** Published data shows approximately 35% of service members who sustain an amputation have it occur at the transfemoral level. Significant evidence indicates microprocessor knees (MPKs) have numerous benefits over non-MPKs for individuals with transfemoral amputation (TFA) including improved gait, safety, comfort, confidence, reduced falls, balance, patient satisfaction and reduced energy expenditure, greater ease in negotiating varying terrains, improvements in multi-tasking and cost effectiveness, such that MPK technology should be considered current state-of-the-art in TFA prosthesis prescription. However, studies which currently exist on MPK technology tend to lump the various knees together as a group rather than teasing out differences between the individual MPK technology and what types of patients are best suited for each. Therefore, a gap exists in clinical knowledge forcing clinicians to choose componentry based on reimbursement or their past experiences with an MPK, rather than detailed evidence supporting the use of one MPK for a certain individual. In this proposal, we will assess the biomechanical function and patient reported outcomes of each subject while they are using three commercially available MPKs and a research grade powered knee, addressing the FY20 OPORP Focus Areas “Prosthetic Device Function” and “Prosthetic Device Form”.

**Hypothesis/Objective:** Our *objective* is to personalize the prosthetic prescription process by creating a clinical decision algorithm for selection of an ideal MPK for an individual patient with transfemoral amputation (TFA) based on objective and patient reported data collected from that specific user. We test the *central hypothesis* that biomechanical and patient perceived differences will be detectable and predictable between different MPK components within a certain individual allowing for the creation of the first ever clinical decision algorithm for MPK component selection.

**Specific Aims:** Aim 1 will assess functional performance associated with use and wear of three different commercially available MPKs and one research grade powered knee in 17 individuals with TFA. Aim 2 will assess subjective patient reported preferences associated with use of the same four prosthetic knees along with collection of subject specific anthropomorphic characteristics that may correlate with MPK choice. Aim 3 will generate the clinical decision algorithm for MPK selection.

**Study Design:** Our study revolves around clinical tests and outcomes measures to evaluate the biomechanical performance and patient reported outcomes of three different commercially available MPKs and a single research grade powered knee in individuals with a TFA. We will test the hypothesis that differences will emerge between individuals when wearing the different knees and that these differences will be predictable. Subjects will ambulate over various terrains to simulate community ambulation with each MPK (Aim 1) allowing for assessment of the functional performance of each MPK. Through collection of individual anthropomorphic data and psychometric outcomes measures (Aim 2), we predict individual preferences and biomechanical improvements will emerge between the various MPKs

allowing for the generation of a clinical decision algorithm for MPKs (Aim 3).

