### Statistical & data analysis plan

A repeated measures ANOVA with within factor MPK will be used to assess differences across treatment for Aims 1 and 2, provided assumptions are met. In the event of missing data or violation, a linear mixed models procedure, which does not assume compound symmetry, will be considered. Bonferroni-Holmes correction will be made to control for family-wise error rate. Samples size calculations are outlined below. Estimated effect size was calculated using Cohen's d for within factor designs [71], assuming a correlation among repeated measures of 0.5. Effect sizes were then converted to Cohen's f for sample size estimations using G\*Power. [72] **Aim 1: Comparison of clinical outcome measures on MPKs.** A Borg RPE of 2 (pooled SD= 2) was deemed clinically relevant for this study, resulting in an effect size of 1. Gait variability index effect size was based upon minimally detectable change (MDC) cited in [73]. An MDC of 8 and hypothesized pooled SD of 6, produced an effect size of 1.3. These data indicate a sample size of approximately 9 will achieve 90% power. The sample size proposed in this study (N=12) should ensure adequate power, even in the event of attrition or slightly higher variability. **Aim 2: Patient reported outcomes.** Resnik & Borgia (2011) have suggested a MDC of 10.3 (90% CI) for OPUS lower limb function.[61] Effect size for this study was calculated using MDC of 10 and a pooled SD of 7.7, assuming higher variability than previously reported SD's for upper

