extremity [73]. This resulted in a Cohen's D of 1.3. Resnik & Borgia (2011) also reported PEQ subscale MDC's which ranged from 0.8-1.4 with Std errors of 0.3-0.6.[61] Based upon an MDC of 1.1 and SD of 1.25, Cohen's d would be 0.88. The sample size of 9 corresponds to 80% power. The SF36V will be used as an additional measure of health related QOL but due to high variability reported in the literature (from the inclusion of both mental and physical function scales)[61], this measure will not be powered by this preliminary study. Instead, this measure will be used to look for clinical trends in the data and aid in potential direction for the future larger study outlined in our transition plan. **Aim 3: Clinical Decision Algorithm.** The creation of the clinical decision algorithm for personalizing the MPK prescription to an individual is an exploratory, informative analysis that is constrained by population size and resources. Repeated sampling is employed to increase the information gained while attempting to minimize within subject variability and provide better examination of relationships. It is expected that in initial development, large effect sizes will be detected which play a critical role in the satisfaction with the use of prosthetic devices. To be valuable to clinical decision making, it is imperative that identification of this causal mechanism include factors other than solely clinical measurements. In addition, proximal outcomes, based on existing knowledge, will supplement the model. This process will lay the groundwork for the decision tree to be refined over time as the sample can be increased. There are a number of models that can be used for this aim (Bayesian approaches, linear discriminant analysis for repeated measures, etc.) which do not require as large a sample size for estimation procedures. The choice of model will be determined based on the underlying data structure by our co-I biostatistician, [name].

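### The plan states that differences between individuals across knees will be predictable, but tests only the average knee effect and does not compare the Aim 3 algorithm with giving everyone the knee that is best on average

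*Combined protocol and SAP*

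**What the plan says.** Section 1 (Study Aim, Background and Design) gives two versions of the hypothesis. The central hypothesis is that "biomechanical and patient perceived differences will be detectable and predictable between different MPK components within a certain individual". The Study Design paragraph goes further: "We will test the hypothesis that differences will emerge between individuals when wearing the different knees and that these differences will be predictable". Both present the algorithm as something that these differences make possible. The Specific Aims paragraph gives the deliverable without a condition: "Aim 3 will generate the clinical decision algorithm for MPK selection".

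In the Statistical & data analysis plan, the named comparison is: "A repeated measures ANOVA with within factor MPK will be used to assess differences across treatment for Aims 1 and 2". A linear mixed model is the fallback for missing data or violated assumptions. Neither is given a term for knee by person or knee by patient characteristic.

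The Aim 3 paragraph of the same section says that creating the algorithm "is an exploratory, informative analysis that is constrained by population size and resources". It adds that "It is expected that in initial development, large effect sizes will be detected", and lists some candidate model families. It then says "The choice of model will be determined based on the underlying data structure by our co-I biostatistician". On what follows, it says: "This process will lay the groundwork for the decision tree to be refined over time as the sample can be increased".

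Nowhere do the documents give a performance measure for the algorithm, a validation method, a comparator, or a result that would count as showing no gain from personalisation.

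**The concern.** Choosing a knee for each patient is worth doing only if it gives better results than giving every patient the knee with the best average result. A difference between knees within a person, which is all that the central hypothesis requires, also arises when one knee is better for everyone, and in that case personalisation adds nothing. The Study Design hypothesis does concern differences between individuals, but no analysis is attached to it.

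The obvious informal check on a finished algorithm is how often it picks the knee on which a person did best, set against 1 in 4. That check does not separate the two situations. With one uniformly better knee, a rule that ignores the patient scores far above 1 in 4. Predicting for left-out people does not cure this, because the average knee effect carries over to new people. What is at stake is the study's stated objective: the algorithm could be carried forward for refinement with no evidence on whether patient characteristics help to choose the knee.

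**Working it through.** **Step 1. What the stated sample size is for.** Inputs from the Statistical & data analysis plan: d = 1 (Borg, 2/2), d = 0.88 (PEQ, 1.1/1.25), correlation ρ = 0.5, n = 9. Section 3 gives m = 4 knees. Two-sided α = 0.05 and sphericity are assumed, as the plan states no α. With f = d/2:

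λ = f² · n · m / (1 − ρ), df = (m − 1, (n − 1)(m − 1)) = (3, 24).

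- d = 1: λ = 0.25 × 9 × 4 / 0.5 = 18.0, power 0.92 (plan: 90%).
- d = 0.88: λ = 0.1936 × 9 × 4 / 0.5 = 13.9, power 0.83 (plan: 80%).

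Nine is the smallest n that reaches the stated power in both cases, so the plan's figure reproduces. It is power for the average knee effect. Nothing is sized or specified for differences between people in which knee is best.

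**Step 2. Could a useless algorithm look predictive?** The plan leaves the model open, so this is an illustration under stated assumptions.

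- Outcome = person effect (variance 0.5) + residual (variance 0.5) + d for one knee. Total SD is 1 and the correlation 0.5. There is no person-by-knee effect.
- N = 17 people, four knees, 11 characteristics unrelated to anything.
- Algorithm: one ridge regression per knee (penalty 5 or 20). The left-out person is assigned the knee with the highest prediction.
- Default: the knee with the highest mean among the other 16 people.
- Measure: agreement with each person's observed best knee. With 17 people, 8 matches are needed to exceed 25% at one-sided p < 0.05 (binomial tail 0.040 at 8, 0.107 at 7).

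| | d = 1, penalty 5 | d = 1, penalty 20 | d = 0.88, penalty 5 | d = 0.88, penalty 20 |
|---|---|---|---|---|
| Agreement, algorithm | 59% | 67% | 53% | 60% |
| Agreement, one knee for all | 68% | 68% | 63% | 63% |
| Trials above 25% | 83% | 95% | 71% | 88% |

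The algorithm beats the default in about 2–6% of trials at d = 1 and 3–6% at d = 0.88. Its true mean outcome at d = 1 is 0.845 (penalty 5) and 0.980 (penalty 20), against 1.000 for the default. The losses are 1.000 − 0.845 = 0.155 SD and 1.000 − 0.980 = 0.020 SD. At penalty 20, about 79% of trials tie, because the algorithm nearly always picks the default knee.

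Even the default reaches only 68%. Noise alone makes the best knee appear to differ between people.

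**Step 3. Sensitivity.**

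- *Simpler model* (three irrelevant characteristics, unpenalised regression, N = 17, d = 1): 62% against 68%, above 25% in 90% of trials, ahead of the default in 4.5%.
- *N = 12*, the size in the power paragraph, same simpler model: 58% against 68%, above 25% in 60%.
- *Two knees equally good and better than the other two* (N = 17, d = 1, ridge): above 25% in 46–52% of trials, ahead of the default in 34–35%.

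**Step 4. Would a simple comparison with the default be safe?** With no knee effect and no personal effect at N = 17, the mean within-person difference favours the algorithm in 44–47% of trials. Its bootstrap 95% interval lies wholly above zero in about 15%. The comparison therefore needs a better-calibrated test than either.

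**The case against.** A reader might infer that the plan will issue an algorithm whatever the data show, or that a uniformly better knee would pass as successful personalisation. The documents do not support either reading. The sentence about generating an algorithm is a statement of a deliverable, not a decision rule. Section 1 makes the algorithm follow from predictable differences, and states those as a hypothesis to be tested. Aim 3 is openly exploratory and a base for later work. No success criterion exists, so there is nothing to pass, and the 1-in-4 benchmark is this review's assumption.

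The illustration can also be challenged. Ridge regression is not among the models that the plan names. The four-knee choice set is not settled: Section 6 speaks of currently available devices, and Section 11 describes the fourth knee as investigational. The plan's d = 1 is a clinically relevant Borg difference, not a forecast that one knee wins. The f = d/2 that reproduces n = 9 is in fact the spread of two knees above two; one above three gives d√3/4 = 0.433d. Under two above two, the result is much weaker. A tie with the default does no harm, and 0.02 SD is negligible.

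Finally, the study collects many outcomes and a survey of each person's priorities. If one knee is better on one outcome and another knee on a second, people with different priorities could suit different knees with no person-by-knee effect on either outcome. A best-mean knee is undefined until an outcome or composite is named.

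All of this limits the size of the point and shapes the fix. It does not supply a test of the between-individual hypothesis or a comparator for the algorithm.

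**Conclusion.** The point holds in a limited form. The plan states a hypothesis about predictable differences between individuals, names a test only for the average knee effect, and gives the exploratory algorithm no evaluation against a non-personalised choice. Followed as written, the study could not tell useful personalisation from one knee being best for everyone.

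The figures show that this confusion can readily happen, not how often it will. They rest on one uniformly better knee, a ridge or simple regression model, uninformative characteristics and agreement as the measure. Under those assumptions at N = 17 and d = 1, above-chance performance is the usual result (83–95% of trials with ridge), while an advantage over the default is rare (2–6%). The harm from following the algorithm is small to modest (0.02–0.16 SD). The exploratory label lowers the seriousness, but the change is cheap and bears on the study's main objective, so it should be made.

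**What to change.** Add to the Aim 3 text in the Statistical & data analysis plan:

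> For a named outcome (or a named composite weighted by the participant's stated priorities) and a stated set of candidate knees, the algorithm will be compared with the policy of giving every participant the knee with the best mean. For each left-out participant, both choices, including any model selection, are derived from the other participants only. The mean within-person difference in observed outcome between the two assigned knees will be reported with a 95% interval, and its p-value will come from permuting participants' characteristics across participants and repeating the whole procedure. Participants missing an outcome on either assigned knee will be counted and reported. The algorithm will be described as supporting personalised selection only if the difference favours it and the permutation test is significant at the stated level; a favourable point estimate or a bootstrap interval alone is not enough. Otherwise the conclusion is that no gain from personalisation was shown in this exploratory sample.

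The sponsor must fill in the outcome or composite, the candidate knees and the significance level before the data are analysed.

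The cost is a few sentences and some extra computing. Each participant is meant to be tested on every knee, so completers supply the outcome under both choices and no new data are needed. The downside is that with 17 people the result will probably be inconclusive, and the study may have to report that no gain was shown.

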## **2. Participant population**

Subjects will be individuals with above the knee and below the hip amputation. This vulnerable population group will be protected through the use of safety equipment such as hand rails and a safety harness for the case of stumbles and falls. The goal is to collect data from at least 17 participants.

### **Inclusion Criteria:**

You may participate in this study if you meet the following criteria:

- A unilateral transfemoral amputation of the lower limb at least six months post fitting of definitive lower extremity prosthesis
- Habitual use of a lower extremity prosthesis in daily living activities (based on assessment of a physiatrist and/or prosthetist and patient self-report)
- Aged between 18 to 75 years
- K3 or K4 level ambulators who can perform all locomotor tasks of interest (based on assessment of a physiatrist and/or prosthetist)

### **Exclusion Criteria:**

You will be excluded from participating if any of the following apply to you:

- Individuals with any significant neuromuscular or musculoskeletal disorder or other comorbidity that would interfere with participation (based on assessment of the physiatrist and/or prosthetist and patient self-report)
- Individuals who have open wounds on their residual limb
- Individuals with known visual impairments that would prevent them from safely operating a prosthesis during over ground walking or ascending stairs (based on assessment of the physiatrist and/or prosthetist and patient self-report)
- Individuals with known hearing impairments or who use hearing aids that would prevent them from responding to an auditory instruction (based on assessment of the physiatrist and/or prosthetist and patient self-report)
- Individuals who are currently pregnant (based on patient self-report) due to slight risk of falling during experiments

All participants that meet the appropriate criteria will be recruited through official flyers and verbal scripts, even if they are already known to the researchers. Flyers will be posted around the campus of Georgia Institute of Technology as well as the general Atlanta community and in partnering clinical facilities, in designated advertising areas. Additionally, word of mouth recruiting will use a script with similar language as the flyers. The study may also be advertised during various outreach events (in-person and/or virtual). Advertisements may be sent out via email lists, patient advocacy websites and online forums, and other online resources including but not limited to our own lab websites. We will also request that our clinical colleagues and collaborators provide interested patients with information about the study and refer them directly to us if their patients are interested in participating.

Recruiting materials are attached as separate documents including a flyer and e-mail script. Permission will be obtained from participants before using any information for research purposes that has individual identifiers attached.

### **3. Study Procedures**

Upon recruitment and informed consent, participants will proceed through the following protocol steps until they have been fit with all 4 prosthetic devices in total.

*Randomization & Blinding:* The order with which each subject will be fit with an MPK will be randomized using a random number generator prior to enrollment. Subjects will not be blinded to device type as appearance of each device is a variable that may influence patient reported outcomes. Blinding of study personnel is not possible given that component-specific knowledge is required to tune each of the different MPKs. Data will be blinded for data analysis procedures to reduce any potential bias.

*Study procedures:*

1. Each device will be measured for length (overall build height) and weight prior to use in the study. Weight of devices will not be controlled due to anticipated effects on the outcomes and thus the final best selection.
2. Anthropomorphic data will be collected from each subject to include cause of amputation, K-level, waist circumference, leg length, residual limb length, build height between distal residual limb and knee center, weight, height, BMI, gender and age. These variables are unique characteristics associated with an individual which may have an impact on their successful use with one device over another. This data will only need to be collected once from each individual participant.
3. Subjects will be administered the Patient Scales of Preference and Importance survey to understand how they individually rank priorities with regards to their prosthetic care and aspects of their daily life. The AMPnoPro will be administered to the subject while they are not wearing their prosthesis to attempt simulation of a patient with a new amputation that has gone through physical therapy and ready for a definitive prosthesis. AMPnoPro has been shown to be predictive of the functional level of an amputee. [1]

Subjects will then undergo fitting and alignment of the prosthetic knees in a randomized order.

4. Acclimation time varies widely in the literature (from 3-10 hours [2, 3] to months [4]) and is acknowledged to have important implications for this study's results. In this study, subjects will go through an initial tuning and training process similar to what is done in clinic scenarios including tuning knee parameters and training over the various terrains in the lab including stairs, ramps and a treadmill. Subjects will then proceed to wear the prosthesis for 1 week at home and in the community in order to acclimate to the device and then return to the lab for testing. A sensor to collect data about the number of steps participants take will be attached to the prosthesis and/or your shoes. This sensor does not have a GPS and will not record where subjects go. Subjects will use their same socket, prosthetic foot and shoe during each knee evaluation to ensure that differences observed during the study are attributable to the knee.
5. Subjects will ambulate five times over the 18' instrumented gait mat to determine their self-selected walking speed (SSWS) and GVI. Subjects will complete a 2-minute walk test and then be administered the Borg RPE.[5] A heart rate monitor will be worn during the 2 minute walk test in order to calculate physiological cost index (PCI) [6]
6. Subjects will proceed to walk up and down an overground 5-degree ramp for ten trials and then walk up/down a 6-step stair case for ten trials while we measure lower body 3D biomechanics and completion speed.

7. Subjects will walk across a beam while wearing the prosthesis. The beam is very low in height and sits only ~2" inches off the ground.
8. Subjects will walk on a treadmill while wearing the prosthesis while we measure lower body 3D biomechanics.
9. Subjects will then fill out the OPUS HRQOL, LEFS, PEQ, Veteran SF-36, and fall history survey to assess their perception of performance and other health related quality of life factors associated with use of each device. Pilot work with these surveys indicates this will take approximately 30-45 minutes.
10. Subjects will repeat Steps 4-8 with periods of rest provided as necessary until they have completed the full protocol for each of the three MPKs and research grade powered knee.

During all testing participants are instructed to vocalize any concerns or discomfort to researchers. Tests that occur in the lab will occur with the use of a safety harness and or gait belt. During tests, verbal feedback from the participants will be used to improve the comfort of the devices. Participants are instructed to notify researchers if they feel unsafe, and may quit the study at any time without penalty. Additionally, participants may be asked to wear EMG sensors, markers for measuring biomechanics and other mechanical sensors (such as IMUs) All participants will be guided through the following general procedure during their visits, requiring action on their part:

- Participants will be briefed about the details of and their rights during the study.
- The prosthesis and attachment interface will be fit to the participant, along with any additional data collection equipment.
- Participants will be guided through the specific activities of the study, detailed already.
- Participants will receive assistance removing any sensors used during the study.

Other equipment may be utilized to measure biomechanics of the user during ambulation. Specifically, we will be using a VICON motion capture analysis system and an instrumented treadmill. This will also us to measure biomechanical similarities and differences while using the powered prosthesis compared to the sound side limb. Also, some protocols will require the use of an EMG (electromyography) system to measure muscle activity across different ambulation tasks. Three systems may be used which includes the Delsys Trigno Wireless EMG system, Biometrics Ltd. EMG system, and COAPT EMG system. All of these systems will use electromyography sensors that will be placed on the surface of the user's skin.

In order to also measure functional clinical measures, a Protokinetics gait mat will be utilized to measure common measures such as step length, step time, and symmetry. This system is just a mat that users will need to walk on top similar to walking overground. Users will be in a harness and have the options for handrails or gait belt if needed.

Throughout the tests there will be a camera recording the session. The purpose of the camera is to record performance for future analysis. The participant will always have the right to stop the test and/or take a break. The participant may also choose to discontinue participation at any time.

During the first visit, fitting and tuning will be no longer than 4 hours. Participants may end the visit at any time without penalty, or choose not to return for additional visits. If the participant agrees to continue the study subsequent visits will be scheduled at their convenience and pending availability of the prosthetic knee joints. During these subsequent visits, testing will last between 2-6 hours based on participant comfort.

Participants will be asked to attend at least 5 sessions in order to compare the effectiveness of the different prosthetic knees. However, each participant will maintain the right to discontinue their involvement for future sessions. Depending on the progress of the tests, participants may be involved in sessions ranging over the course of a few months.

The results of the study will be in the form of device performance and participant feedback. Sensor data will record the movement parameters of the subject. This includes mechanical instruments on the device and biomechanical instruments attached to both the device and the human subjects. These instruments will give information about the kinematics (movement), kinetics (force), muscle activity, step count, heart rate and metabolics of the user. This allows for the effectiveness of the design strategy to be assessed. The participants will also give feedback in the form of verbal conversation. This verbal feedback will deal with the comfort, convenience and preferences of the devices and controllers.

This study will use statistical analysis to compare between different intent recognition systems. We will use intent recognition accuracy as the primary metric to compare statistical differences across conditions. We will compare biomechanics between the powered device and a passive prosthesis. Typically, ANOVA tests are used with repeated measures to compare across multiple conditions.

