## **11. Investigator's Qualifications**

The PI, [name], has conducted a number of experiments similar to this one with amputees. The Co-PI, [name], is a certified prosthetist specifically trained to work with individuals with amputation and fit prosthetic devices to them. Three of the prosthetic knees used in this protocol are clinically available through manufacturers and used broadly in the prosthetics clinical community. These are the devices that will be brought home for 1 week testing protocols with participants. The fourth device is our own experimental investigational device and the testing of this device was IRB approved previously at Georgia Tech with a separate, but related protocol. All members listed on this IRB protocol have CITI training.

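### Knee order is randomised with no stated balance on position or preceding knee; with 17 participants marked chance imbalance is likely, and a Williams-square list removes nearly all of it at little cost

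*Combined protocol and SAP*

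**What the plan says.** Section 3 (Study Procedures), under Randomization & Blinding, states: "The order with which each subject will be fit with an MPK will be randomized using a random number generator prior to enrollment". No block, Latin square or other restriction is given there or elsewhere.

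Participants continue "until they have been fit with all 4 prosthetic devices in total". For each knee, step 4 describes tuning and training, then: "Subjects will then proceed to wear the prosthesis for 1 week at home and in the community in order to acclimate to the device". Step 10 moves on to the next knee: "Subjects will repeat Steps 4-8 with periods of rest provided as necessary". No washout or return to the usual knee is described.

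On visits, section 3 says: "Participants will be asked to attend at least 5 sessions in order to compare the effectiveness of the different prosthetic knees". It also makes scheduling depend on the participant's convenience and on which knees are available.

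The Statistical & data analysis plan specifies a repeated measures ANOVA with knee as the within-subject factor, or a linear mixed model if data are missing or assumptions fail. It names no term for position, sequence or carry-over.

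Two inconsistencies affect this point:
- **Sample size.** Section 2 says "The goal is to collect data from at least 17 participants", but the analysis plan says "The sample size proposed in this study (N=12) should ensure adequate power".
- **Home wear.** Step 4 reads as if every knee is worn at home. Section 11 says of the three commercial knees: "These are the devices that will be brought home for 1 week testing protocols with participants".

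**The concern.** In a four-period crossover, a knee's result can depend on when it was tested (practice, fatigue, familiarity with the tasks) and on which knee came before it (habits, soreness, contrast). Randomising the order makes these influences average out over hypothetical repetitions of the trial. This trial will use a single list of about 17 orders, and any imbalance in that list stays in the results.

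If knee A happens to follow the powered knee often and knee B seldom, the A minus B difference contains part of the powered knee's after-effect. The same holds for position if A is often tested first and B is not. The planned model has no term that could absorb either influence. At stake are the knee contrasts of Aims 1 and 2, which also inform Aim 3.

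**Working it through.** **Inputs.** Knees: 4 (section 3). Participants: 17 (section 2), with 12 (analysis plan) as the alternative. Model: knee only (analysis plan). Assumption: each order is drawn independently and uniformly from the 24 permutations. The size of carry-over is not given, so it is left as L.

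**The plan's own figures.** The documents give none for order balance. The nearest is the sample size of about 9. Using noncentrality λ = n·m·f²/(1−ρ), with m = 4, ρ = 0.5, f = d/2 and an assumed alpha of 0.05:
- Borg RPE: d = 1, f = 0.5, λ = 9·4·0.25/0.5 = 18, power 92%. The plan states 90%.
- PEQ: d = 0.88, f = 0.44, λ = 9·4·0.1936/0.5 = 13.9, power 83%. The plan states 80%.

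In both cases 9 is the smallest n that reaches the stated power, so the figures reproduce.

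**Can one knee directly follow another?** With separate fitting and test visits, four knees need 8 sessions. Five suffice if each middle visit tests one knee and fits the next. Five is a stated minimum, so direct hand-overs are possible but not established.

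**Counts with 17 independent orders (simulation).** A given knee directly precedes another given knee with probability 3/12 = 1/4 per participant. The pair count therefore has mean 17/4 = 4.25 and SD √(17·¼·¾) = 1.8. Each knee-by-position count has the same mean and SD.

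| Event | Share of realisations |
|---|---|
| Some knee in some position at most once | about 55% |
| Some knee in one position 8 or more times | about 47% |
| Some ordered pair at most once | about 47% |
| Some ordered pair never | 8–9% |
| Some ordered pair 8 or more times | about 39% |

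These are extremes over 16 cells or 12 pairs. For one named knee, the chance that it follows one predecessor at least three times as often as another is 37%. For at least one of the four knees it is 81%. With N = 12, some pair never occurs in 32% of realisations.

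**Bias under the knee-only model.** Suppose knee k adds L to whatever follows it. The contrast of two other knees i and j is then biased by L·(n_ki − n_kj)/N, where n_ki counts how often k directly precedes i. Per participant the difference is +1 or −1 with probability ¼ each, so its variance is ½.
- Random order, N = 17: SD = L·√(0.5/17) = 0.17L. The 95th percentile of the absolute bias is 6/17 = 0.35L.
- Random order, N = 12: SD = L·√(0.5/12) = 0.20L.
- Williams set, N = 17: counts differ by at most 1, so the bias is at most 1/17 = 0.06L.

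The same arithmetic applies to an effect P confined to one position: SD 0.17P under random order, at most 0.06P when balanced.

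**Variance of a knee contrast, N = 17 (units of error variance).**

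| Terms in model | Random order, mean | Williams set | Ratio |
|---|---|---|---|
| Knee (and participant) | 2/17 = 0.118 | 0.118 | 1.00 |
| + position | 0.126 | 0.118 | 1.07 |
| + first-order carry-over | 0.150 | 0.130 | 1.15 |

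A ratio of 1.07 is worth 17·(1 − 1/1.07) = 1.1 participants, and 1.15 is worth 17·(1 − 1/1.15) = 2.2.

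**What balance leaves behind.** No knee follows itself. In a Williams set each knee follows each other knee in a quarter of participants, so third knees cancel in the i minus j contrast, but i and j affect each other. The remaining bias under the knee-only model is (L_j − L_i)/4.

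**The case against.** The strongest counter-argument is that the harm may be small. Every commercial knee has tuning, training and a week of wear before testing, and that week may act as an active washout. The plan calls it acclimation, but it is still some protection, so order is not the only safeguard. L is not estimated anywhere and may be minor by the test visit. This objection stands, and it limits how strongly the point can be put.

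A reader might infer that five sessions prove back-to-back changes of knee. They do not: five is a minimum, and on section 11's wording the powered knee may need no home week.

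A reader might also infer that the trial loses 15% efficiency, or about 2 of 17 participants. That loss arises only if a carry-over term is fitted, and none is planned. On the plan's own reckoning, where 9 participants suffice, such a loss would not threaten power anyway.

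Nor does a balanced list cure carry-over. The (L_j − L_i)/4 term remains. If one of the two compared knees carries over by L, that is 0.25L, more than the 0.17L SD that balancing removes. Each participant still has only one order, so the person-level choice of knee in Aim 3 stays confounded with that order.

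Finally, a random number generator could also be used to produce a balanced list. The documents support the statement that no balance is stated, not that none will be used.

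**Conclusion.** The point holds as a design improvement worth making, not as a flaw that invalidates the trial. No balance on position or predecessor is stated, no washout is stated, and the model has no term for either. Under independent draws, marked imbalance in a list of 17 is about as likely as not by the counts above, and pair coverage is worse at 12. The consequence under the planned analysis is chance bias, with SD about 0.17 of whatever carry-over or single-position effect exists, which a balanced set cuts to at most 0.06 for comparisons not involving the knee that carries over. Variance is affected only if position (about 7%) or also carry-over (about 15%) is modelled.

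This rests on independent uniform draws, which are inferred from the absence of any stated restriction, and on full follow-up. The absolute size of the bias cannot be given because L is unknown. Carry-over onto the powered knee may be the least protected, depending on how the two statements on home wear are reconciled.

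**What to change.** 1. Replace the sentence on order in section 3, Randomization & Blinding, with: participants are allocated at random, in blocks of 4, to the four sequences of a Williams square, with knee labels assigned to the square at random once. Each knee is then in each position, and directly follows each other knee, 4 or 5 times among 17, or exactly 3 times if N is 12.
2. Record what was worn before each fitting, and any departure from the assigned order.
3. In the analysis plan, add position to the model for Aims 1 and 2, with first-order carry-over as a sensitivity analysis. State for Aim 3 that order remains confounded with the individual's choice of knee.
4. Reconcile section 3 step 4 with section 11 on whether the powered knee is worn at home, and settle whether N is 17 or 12.

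**Cost.** A different list before enrolment, or for the remaining participants if enrolment has begun. No more participants or planned visits are needed. Keeping to an assigned order may take some scheduling effort because visits depend on knee availability, and dropout would disturb the balance somewhat.
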